If nonintubation anaesthesia for laryngomicrosurgery can be performed with nerve block and intravenous anesthetic medicine, the cardiovascular risks may decrease because of avoiding CO2 retention by maintaining patient's spontaneous breathing function. The feasibility and safety of nonintubated LMS with spontaneous breathing was evaluated in this case series.

Method

We divide the patients who need laryngoscopy microsurgery into three groups. The first group is general anesthesia with endotracheal tube intubation, the second group is non-intubation with muscle relaxant administered; the third group is non-intubation without muscle relaxant.

The three groups will perform arterial blood oxygen analysis (collecting PaO₂, PaCO₂, pH, HCO₃-data) before intubation, before muscle relaxant administration and before SLNB, after the operation and 15 minutes after transferring to the recovery room, as well as the pressure of the surgeons and the degree of completion of the operation to analyze the difference between intubated general anesthesia and non-intubation anesthesia.

Results

Last year, we passed the in-hospital plan (2021/04/07) and have been included (Table 1). There are 15 males and 14 females, all of whom have completed the trial phase without complications. Group 1 earns 11 people, Group 2 earns 7 people, and Group 3 earns 11 people.

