During the operation, a pulse oximeter will be used to monitor and record the patient's oxygen saturation. The patient's gender, height, weight, BMI, age, past medical history, ASA classification, type of laryngoscopic surgery, operation time, lesion location, blood loss, and anesthesia records will be kept.

All three groups of patients will use radial artery catheters. In addition, the three groups performed arterial blood gas analysis (including: PaO₂, PaCO₂, pH, HCO₃⁻) at the following times to understand the difference of pCO₂ in different groups and as a secondary result.

The first period to measure those variables is before each set of surgery are follows:

The first group is before tracheal intubation.

The second group was before the administration of muscle relaxants.

The third group is before applying superior laryngeal nerve block bilaterally.

The second period to measure those variables is the end of the operation.

The third period to measure those variables is 15 minutes after entering the recovery room.

All the anesthesia time, operation start time and operation end time of the three groups will be recorded, and the relationship between them will be discussed.

After the operation, the surgeon and the patient will be asked to do a questionnaire survey in order to understand whether the non-intubation anesthesia laryngoscope microsurgery of the self-breathing causes obstruction or other difficulties for the operator, as well as the patient's postoperative recovery, surgical satisfaction and operation After scoring. Finally, the surgeon's score on the degree of surgical completion was taken as the primary outcome.

Conditions for participating in this research project:

- Subjects are between 20-80 years old.
- Patients undergoing laryngoscope microsurgery.

- Anesthesiologists rated ASA as between I and III.

If those who are included have any of the following conditions, you will not be able to participate in this research project:

- Having drug dependence and drinking habits.
- Abnormal heart, liver and kidney function.
- Allergic reactions to narcotic drugs.
- Emergency surgery.
- pregnancy.
- Refuse to participate.

This study will explore the following assumptions:

Ho1: The intraoperative field of vision of the nonintubation group is clearer than that of the intubation group.

Ho2: Non-intubation and no muscle relaxation has less carbon dioxide retention and less hypercapnia.

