NBPd	83.8	9.7	83.3	9.1	71.6	14.5	0.06
PR	69.8	7.5	71.4	16.0	72.3	10.2	0.46
RR	14.7	2.9	15.6	4.0	15.8	2.6	0.79
In surgery							
SpO2	98.4	1.0	98.1	1.8	97.9	2.2	0.96
NBPs	128.7	19.7	133.3	16.2	123.8	16.4	0.45
NBPd	80.2	11.4	72.9	9.2	71.4	10.2	0.15
HR	83.8	15.1	90.4	9.6	88.4	13.3	0.54
After surgery							
BT	36.2	0.5	36.0	0.1	36.0	0.4	0.26
SpO2	98.9	1.4	98.9	1.1	98.3	2.3	0.85
NBPs	138.5	26.5	117.0	13.4	124.4	6.4	0.20
NBPd	85.5	16.8	77.3	14.8	78.0	8.5	0.26
PR	83.5	6.6	81.1	12.6	89.1	13.2	0.46
RR	15.4	3.0	16.1	4.0	15.8	2.8	0.63
PAR Score	8.8	1.7	7.1	2.1	7.8	2.1	0.15

Table V. The heartbeat of group 2 tends to rise during the operation

Table VI. Operation status

Variable	G1(n=11)		G2(n=7)		G3(n=11)		p-value
	Mean	SD	Mean	SD	Mean	SD	
OP time	77.4	35.8	37.3	8.1	39.7	21.4	0.00
	n	(%)	n	(%)	n	(%)	
LMS Procedures							
Vocal polyp	1.0	9.1	1.0	14.3	3.0	27.3	0.14
Vocal cyst	4.0	36.4	2.0	28.6	0.0	0.0	
Vocal atrophy	1.0	9.1	2.0	28.6	0.0	0.0	
Vocal paralysis	0.0	0.0	0.0	0.0	0.0	0.0	
Laryngeal tumor	1.0	9.1	0.0	0.0	0.0	0.0	
Other	4.0	36.4	2.0	28.6	8.0	72.7	
Lesion site							
Ant.	3.0	27.3	0.0	0.0	0.0	0.0	0.16
Middle	4.0	36.4	3.0	42.9	5.0	45.5	
Post.	1.0	9.1	0.0	0.0	2.0	18.2	
Mixed	1.0	9.1	0.0	0.0	0.0	0.0	
Ant & Middle	2.0	18.2	1.0	14.3	0.0	0.0	
other	0.0	0.0	3.0	42.9	4.0	36.4	
Surgery completion							
Complete	11.0	100.0	7.0	100.0	11.0	100.0	N/A
Partially complete	0.0	0.0	0.0	0.0	0.0	0.0	
Incomplete	0.0	0.0	0.0	0.0	0.0	0.0	
Vision							
Good	10.0	0.9	7.0	100.0	10.0	0.9	0.71
Poor	1.0	0.1	0.0	0.0	1.0	0.1	
Poor Visualization							
none	10.0	90.9	7.0	100.0	10.0	90.9	0.51
Difficulty with vocal cord injection	0.0	0.0	0.0	0.0	1.0	9.1	
Other	1.0	9.1	0.0	0.0	0.0	0.0	
The Cormack-Lehane (CL) glottis view classification							
I	9.0	81.8	6.0	85.7	9.0	81.8	0.97
IIa	2.0	18.2	1.0	14.3	2.0	18.2	
IIb	0.0	0.0	0.0	0.0	0.0	0.0	
III	0.0	0.0	0.0	0.0	0.0	0.0	
IV	0.0	0.0	0.0	0.0	0.0	0.0	
Laryngeal compress							
Not applied	1.0	9.1	0.0	0.0	0.0	0.0	0.43
Applied	10.0	90.9	7.0	100.0	11.0	100.0	
N/A : Not suitable for any statistics.							

Table VI. Among the three groups of operation time, the operation time of the first

group was longer than that of the other two groups.

Table VII. Surgeon's Feedback

Variable	G1(n=11)		G2(n=7)		G3(n=11)		p-value
	n	(%)	n	(%)	n	(%)	
Satisfaction							
Satisfied	11.0	100.0	7.0	100.0	10.0	90.9	0.43
Partially satisfied	0.0	0.0	0.0	0.0	1.0	9.1	
Unsatisfied	0.0	0.0	0.0	0.0	0.0	0.0	
	Mean	SD	Mean	SD	Mean	SD	
Stress index	1.0	0.0	1.9	1.2	2.0	0.8	0.01

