Table VII. The surgeon was satisfied with the surgical satisfaction of the three groups, but the stress intensity was higher when performing non-intubation and nerve block surgery.

Table VIII. Dunnett T3 Post-hoc tests of during the operation

variable			M.D (I-J)	SE	p-value
pH_2	G1	G2	.135961*	.024404	.001
		G3	-.013455	.017469	.825
	G2	G1	-.135961*	.024404	.001
		G3	-.149416*	.024411	.000
	G3	G1	.013455	.017469	.825
		G2	.149416*	.024411	.000
PaCO2_2	G1	G2	-32.0468*	8.5162	.020
		G3	-1.1636	3.9766	.987
	G2	G1	32.0468*	8.5162	.020
		G3	30.8831*	8.8281	.023
	G3	G1	1.1636	3.9766	.987
		G2	-30.8831*	8.8281	.023
PaO2_2	G1	G2	-134.9130	52.1401	.087
		G3	-155.0273*	45.5545	.012
	G2	G1	134.9130	52.1401	.087
		G3	-20.1143	63.6399	.984
	G3	G1	155.0273*	45.5545	.012
		G2	20.1143	63.6399	.984

*. The M.D is significant at the 0.05 level.

[figure not shown]
Table VIII. Found the following situation :

1. In the non-intubated and muscle relaxant group (G2), the pH value during the operation was lower than the non-intubated and nerve-blocking group (G3), and lower than the normal value (7.35-7.45) .
2. During the operation, the PaCO2 of the non-intubated and muscle relaxant group (G2) was significantly higher than intubated group and also higher than the non-intubated and nerve-blocking group.
3. The PaO2 value of the intubation group (G1) during the operation was lower than that of the non-intubation group.

KSVGH20-C9-09 CASE REPORT

No:	Consent Signed _(MM/DD/YYYY) :	Operation Date:				
Patient status : _____						
Reason for quitting :						
Gender:	Age:	Weight _(kg) :	Height _(cm) :	BMI:	ASA:	
BASELINE MEDICAL/SURGICAL HISTORY :						
Time to enter the room :		Before induction BT:_____ SpO ₂ :_____ BP:___/___ PR:___ RR:___				
Study Group		Operation time				
Induction time		Anesthesia time				
Endo size & pressure		Propofol dose		Rocuronium dose		
		Fentanyl dose		Cisatracurium dose		
GAS		Before(:) G1: intubation ; G2: cis and scc ; G3: SLNB		OP end(:)		
pH				POR(:)		
PaCO ₂						
PaO ₂						
SO ₂ %						
HCO ₃ ⁻						
Time to post anesthesia recovery room :						
BT:_____ SpO ₂ :_____ BP:___/___ PR: ___ RR:_____						
PACU	Time	oxygen	respiration	circulation	consciousness	activity

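### The case report form has no field for intraoperative SpO2 or heart rate, and Table V does not define its in-surgery value, so brief desaturation cannot be read from the dataset

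*Protocol*

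**What the plan says.** Section C of the Protocol (Methods and study procedure) says: "During the operation, a pulse oximeter will be used to monitor and record the patient's oxygen saturation". It gives no recording interval, summary measure or threshold. The same paragraph lists items to be retained, ending with "blood loss, and anesthesia records will be kept".

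The case report form has one set of vital signs before induction and a second beside the entry "Time to post anesthesia recovery room". Its other oxygen items are the blood gases (before, operation end, recovery room) and a recovery-room score. The text shown has no box for SpO2 or heart rate during surgery.

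Table V, an interim summary of 29 patients, has an in-surgery block with one row per variable, each giving mean and SD for groups 1, 2 and 3 and a p-value. Saturation reads "SpO2 98.4 1.0 98.1 1.8 97.9 2.2 0.96" and heart rate "HR 83.8 15.1 90.4 9.6 88.4 13.3 0.54". The note below the table says: "The heartbeat of group 2 tends to rise during the operation".

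On purpose, the opening summary says: "The feasibility and safety of nonintubated LMS with spontaneous breathing was evaluated in this case series". Its Results part makes blood oxygen change during the operation a comparison of interest, and the sample size paragraph includes complications in the main purpose.

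**The concern.** Under the Methods, group 2 stops breathing on high-flow nasal oxygen and group 3 breathes spontaneously without a tube. What happens to oxygenation between the start and end of surgery therefore bears on the safety aim. The only tabulated intraoperative SpO2 is a value whose meaning is not given, and the form has nowhere to enter one. A nadir and an average support opposite safety statements from the same row, and a later reader could take either. The heart-rate remark rests on an equally undefined reading and names one group only.

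**Working it through.** The point concerns data capture, so there is no design figure to reproduce. The checks use Table V.

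**1. Lowest single SpO2 compatible with the in-surgery row.** With n values of mean m and sample SD s, no value can be lower than m − s(n − 1)/√n.

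- Group 1 (n = 11): 98.4 − 1.0 × 10/√11 = 95.4%
- Group 2 (n = 7): 98.1 − 1.8 × 6/√7 = 94.0%
- Group 3 (n = 11): 97.9 − 2.2 × 10/√11 = 91.3%

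Taking the rounding at its least favourable (mean 0.05 lower, SD 0.05 higher) gives 95.2, 93.9 and 91.1%. So no tabulated value is below about 91%.

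**2. What that means under each reading.** If each value is the patient's lowest, none of the 29 fell below about 91%. If it is an average or a spot value, the bound applies to that summary and not to the trace. As an illustration with assumed values, take the group 3 mean operation time of 39.7 (Table VI, read as minutes) with SpO2 at 98% except for 2 minutes at 85%. The time average is (37.7 × 98 + 2 × 85)/39.7 = 97.3%, which fits the group 3 row easily. A nadir of 85% could not appear in that row.

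**3. Can the blood gas decide?** The Methods place the second arterial sample at the end of the operation, although Table II labels it in surgery. One sample at that point cannot show a fall that has already recovered.

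**4. Heart rate, before to in surgery.**

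- Group 1: 83.8 − 69.8 = +14.0
- Group 2: 90.4 − 71.4 = +19.0
- Group 3: 88.4 − 72.3 = +16.1

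All three rise, and the largest and smallest changes differ by 5.0. The SD of the change is not reported, so the changes cannot be tested from the table.

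**5. Reported p-values.** One-way ANOVA from the summary statistics gives F = 0.61, p = 0.55 for in-surgery heart rate (stated 0.54, in agreement). For SpO2 it gives F = 0.23, p = 0.79 (stated 0.96). ANOVA does not reproduce the latter; a rank test may have been used. Neither p-value affects the point.

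**The case against.** The strongest reply is that nothing has been lost. The Methods say saturation is recorded and anesthesia records are kept. Table V holds intraoperative values, so some source beyond the form was used. Blood loss is also listed as kept and has no field on the form shown, so a missing box does not prove uncollected data. The form's layout may also have suffered in text extraction. The named respiratory endpoints are carbon dioxide retention or hypercapnia and postoperative lung complications, not desaturation. The arterial comparison has defined sampling times and fields. A desaturation definition could sit in an analysis plan that is not at hand.

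Most of this stands, and it limits the point to extraction and definition. It does not tell the reader what the Table V value is, and an analysis plan does not by itself add a field to the form.

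Some stronger readings are tempting but unsupported:

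- **Desaturation goes unseen.** The retained records argue against this.
- **A favourable reading was picked, perhaps differently by group.** The Protocol says nothing of the kind.
- **The pulse reading must come from a different moment than the arterial sample, because the two order the groups oppositely** (98.4/98.1/97.9 against 99.3/99.6/99.7). The spreads are only 0.5 and 0.4 points, with p = 0.96 and 0.48, and the methods of measurement differ. The in-surgery SpO2 order also repeats the pre-surgery order (98.8/98.1/97.7).
- **The heart-rate note is false.** Group 2 does rise, and by the most; the note is incomplete because it omits the other groups.

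**Conclusion.** The point holds as a modest data-capture defect. The Protocol promises recording of intraoperative SpO2, its form gives that recording no field, and Table V leaves its summary undefined. The interim row therefore either excludes falls below about 91% or says nothing about brief falls, and the document does not say which. This applies to all three groups, intubated and non-intubated alike. No desaturation rate, hidden or otherwise, can be inferred. The conclusion assumes that the form text shown is complete and that the Table V means and SDs are correct to their printed rounding.

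**What to change.** Add an intraoperative block to the case report form, filled from the existing monitor or anesthesia record from induction to operation end, identically in all groups. It should hold lowest SpO2, whether SpO2 fell below a stated threshold, and for how long. Below 90% is one possible reporting level, since the form's recovery score already uses it; that score also uses 92% on room air, so the choice should be stated. It serves as a reporting definition only, not a rule for managing patients.

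Report lowest SpO2 and the number of patients below the threshold by group, in place of the in-surgery SpO2 mean. Say what the in-surgery heart rate is and report its change from baseline for all three groups, as item 2 of the Statistical analysis already plans, and extend the Table V note accordingly.

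Of the planned 90 patients, 90 − 29 = 61 remain, so most of the data can be captured prospectively. The first 29 can be back-filled where records allow, with the number not recoverable stated by group. The cost is a little more data extraction and possibly a less favourable safety table.

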10. Yang SS, Wang N-N, Postonogova T, Yang GJ, McGillion M, Beique F, Schricker T. Intravenous lidocaine to prevent postoperative airway complications in adults: a systematic review and meta-analysis. British journal of anaesthesia 2020.

表單 G4

C METHODS AND STUDY PROCEDURE

We expect to treat patients from 20 to 80 years of age who need to undergo laryngoscope microsurgery and are divided into three groups, the first group: the intubation general anesthesia group, and the second group, the third group two non-intubation Anesthesia group.

Patients in the intubation general anesthesia group will receive intravenous anesthesia using target-controlled infusion (TCI) propofol and remifentanyl, and they will be given intravenous 0.2 mg glycopyrolate and 40 mg methylprednisolone and 5 mg midazolam. After losing consciousness, give cisatracurium 0.15mg/kg, and then perform endotracheal intubation (5.0-5.5, I.D. mm). After the endotracheal intubation is completed, it will be transferred to the respirator for positive pressure ventilation and maintained until the end of the operation.

[figure not shown]
Patients undergoing non-intubation anesthesia for laryngoscope microsurgery will use transnasal humidified rapid-insufflation ventilator exchange (THRIVE) and target-controlled infusion (TCI) intravenous anesthesia with propofol and remifentanyl. The laryngoscopy microsurgery operation will be divided into two groups: the group administrate muscle relaxants, and the group maintain spontaneous breathing without administering muscle relaxants.

After installing the monitor, Optiflow 100% 20L/min oxygen was used to pre-oxygenation through the nasal device for five minutes, and the patient was given intravenous injection of 0.2 mg glycopyrolate and 40 mg methylprednisolone and 5 mg midazolam.

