The second group: the group using muscle relaxants will first give a low dose of cisatracurium about 1.5-3mg, and after the effect of Propofol TCI loses consciousness, 0.6mg/kg Rocuronium or 0.1mg/kg Cisatracurium will be administered. When the patient stops breathing, Optiflow is adjusted to 50L/min and maintained until the end of the operation, the patient resumed spontaneous breathing. The patient's head will strengthen and ensure that the airway is stable, and the laryngeal

microscope will erect and reveal the location of the lesion to facilitate surgery. Low-dose muscle relaxant succinylcholine will be given continuously to maintain muscle relaxation until the end of the operation.

The third group: the group without the muscle relaxant will first touch the rear of the hyoid bone to the greater cornu about 0.5-1cm below the inner side of the greater hornu, that is, the internal branch of superior laryngeal n(chart I). Injection through the thyrohyoid membrane 1% Lidocaine 1-2ml for bilateral Superior laryngeal nerve block, and intravenous injection of Lidocaine 1-1.5mg/kg, Propofol TCI occurs.

(chart I)

The patient loses consciousness after setting up the laryngoscope, and 10% Lidocaine spray is used for intratracheal spray. After the effect is produced, the operation can be performed. Optiflow is adjusted to 50 L/min and maintain until the end of the operation.

After the operation, Propofol TCI and remifentanil TCI are stopped to wake up the patient, and Optiflow is adjusted to 15-20L/min. Patients who are given muscle relaxants will be given 1 mg of Atropine and 2.5 mg of neostigmine after spontaneous breathing is restored. After the patient resumes complete spontaneous breathing, Optiflow is stopped, the patient will be put on an oxygen mask, and transferred to a postanaesthesia care unit PACU for postoperative observation. After leaving the PACU, the patient will be transferred to the general ward to observe for one night.

Target-controlled infusion (TCI) injection of propofol will be set to Schneider model, Ce-targeted: 2.0-4.0 ug/ml, remifentanil 2–6 ng/ml. GE Entropy EasyFit Sensor was used to monitor intraoperative State Entropy (SE), Response Entropy (RE) and

Surgical plethysmographic index (SPI), and as a reference for adjusting TCI propofol and remifentanyl.

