Ho3: There is less sore throat in the nonintubation group than in the intubation group.

Ho4: Non-intubation and no muscle relaxation may lead to less postoperative pulmonary complications.

Ho5: In the non-intubation group, no muscle relaxants are more suitable for long-term surgery than those with muscle relaxants.

Statistical analysis (the statistical analysis tool will use IBM SPSS version 20):

- 1 、 The sample characteristic data will be expressed as average, SD, and median, and the category variables will be displayed in the form of count and percentage.
- 2 、 The 95% confidence interval will show the original data and the change from the baseline.
- 3 、 The difference between the three groups was analyzed using one-way ANOVA to analyze the comparison between the intubation and non-intubation groups for drug administration, the presence or absence of complications, the severity and

the degree of completion of the operation.

- 4 ‧ The differences between the groups will be evaluated by chi-square test or Fisher's exact test.
- 5 ‧ Unless otherwise stated, all statistical tests will be two-way and evaluated at a significance level of 0.05.

Sample size calculation :

The main purpose of the study will focus on the completion of surgery and the occurrence of complications. In order to obtain the total number of participants in the study, a sample size will be calculated to detect a difference in incidence reduction of 25%. A statistical power of 80%, a 5% alpha and up to 10% possible sample loss. Therefore, each group will require 30 patients (90 in total). Considering the number of patients undergoing laryngoscope microsurgery each year, we estimate that there may be a total of 45 patients within a year. After meeting the inclusion criteria and obtaining patient consent, 45 patients will be included in the treatment plan in the first year, and the remaining sample size will be completed next year.

Primary outcome(2nd year) :

- 1 ‧ Less carbon dioxide retention and less hypercapnia.
- 2 ‧ Reduce postoperative lung complications.

Statistics from 10/20/2020 to 5/11/2021 :

Table I-i. Baseline demographics

Variable	G1(n=11)		G2(n=7)		G3(n=11)		p-value
	Mean	SD	Mean	SD	Mean	SD	
Age	52.0	13.9	46.9	8.4	51.7	14.2	0.66
BMI	26.4	5.5	24.5	3.5	25.1	2.5	0.78

Table I-ii. Baseline demographics

Variable	G1(n=11)		G2(n=7)		G3(n=11)		p-value
	n	(%)	n	(%)	n	(%)	
Sex							
male	7.0	63.6	3.0	42.9	5.0	45.5	0.60
female	4.0	36.4	4.0	57.1	6.0	54.5	
ASA							

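### The first blood gas is timed by a different event in each group, so change from baseline in PaCO2 has no common reference point

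*Protocol*

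**What the plan says.** Protocol section C (Methods and Study Procedure) sets three gas samples: before surgery, at the end of the operation, and 15 minutes after arrival in recovery. The last two are common to all groups. The first is not:

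- G1 (intubation): "The first group is before tracheal intubation"
- G2 (no tube, with relaxant): "The second group was before the administration of muscle relaxants"
- G3 (no tube, nerve block, no relaxant): "The third group is before applying superior laryngeal nerve block bilaterally"

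The case report form prints the same three group-specific triggers beside the first gas column, and the Method part of the abstract repeats them.

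Item 2 of the Statistical analysis list says: "The 95% confidence interval will show the original data and the change from the baseline". It does not name PaCO2. Where section C describes the gas sampling, it treats the pCO2 difference as secondary. The second-year outcome list after the sample size paragraph places less CO2 retention and hypercapnia under primary outcome.

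**The concern.** A change score compares groups fairly only if its starting value means the same thing in each. Here the starting value is tied to steps that sit at different places in the three anaesthetic sequences, and CO2 retention is what the groups are compared on. Drugs that depress or stop breathing may come before the first sample in one group and after it in another. The change from baseline, and the before-surgery rows of Table II, would then compare different states. Analysis cannot repair this later, because a common baseline that was never sampled cannot be reconstructed.

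**Working it through.** **1. Where each landmark falls (section C).**

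- G1: "After losing consciousness, give cisatracurium 0.15mg/kg, and then perform endotracheal intubation". Intubation is the last of three steps. A sample taken awake, under hypnosis or after the relaxant would each comply, because the rule sets only a latest time.
- G2: the text "will first give a low dose of cisatracurium about 1.5-3mg, and after the effect of Propofol TCI loses consciousness", and the main relaxant dose follows. The landmark could mean before the low dose (before loss of consciousness) or before the main dose (after it). The form's label names the drugs but not which dose.
- G3: lidocaine is injected "for bilateral Superior laryngeal nerve block, and intravenous injection of Lidocaine 1-1.5mg/kg, Propofol TCI occurs". The block is written before propofol.

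Oxygen before the first sample also differs on paper. For the non-intubation groups, "Optiflow 100% 20L/min oxygen was used to pre-oxygenation through the nasal device for five minutes"; no such step is described for G1.

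**2. Inputs.** Table II, PaCO2 in mmHg, mean (SD), n = 11/7/11. Table II heads the second block as in surgery; I take it as the end-of-operation sample defined in section C and on the form.

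| Sample | G1 | G2 | G3 |
|---|---|---|---|
| 1, before surgery | 49.5 (2.5) | 53.6 (9.5) | 51.3 (6.5) |
| 2, operation end | 54.4 (7.6) | 86.4 (21.7) | 55.5 (10.8) |
| 3, recovery | 43.6 (4.0) | 45.1 (9.0) | 43.3 (5.7) |

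**3. Reproducing Table VIII (raw sample 2).** SE = sqrt(s1²/n1 + s2²/n2).

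- G2 − G1: 86.4 − 54.4 = 32.0, SE = sqrt(21.7²/7 + 7.6²/11) = 8.516. Stated: 32.0468, SE 8.5162.
- G2 − G3: 86.4 − 55.5 = 30.9, SE = sqrt(21.7²/7 + 10.8²/11) = 8.825. Stated: 30.8831, SE 8.8281.

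Both agree to rounding, so the reported contrasts use raw values.

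**4. Changes within group.**

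| Quantity | G1 | G2 | G3 |
|---|---|---|---|
| Sample 2 − sample 1 | +4.9 | +32.8 | +4.2 |
| Sample 2 − sample 3 | +10.8 | +41.3 | +12.2 |
| Sample 1 − sample 3 | 5.9 | 8.5 | 8.0 |

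The second row treats recovery as the undisturbed level, which is an assumption. With an assumed common awake value of 40 to 44 mmHg instead, the rises are 14.4 to 10.4 (G1), 46.4 to 42.4 (G2) and 15.5 to 11.5 (G3).

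**5. Contrasts between groups.**

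| Contrast | Change from sample 1 | Raw sample 2 | Change from recovery |
|---|---|---|---|
| G2 − G3 | 28.6 | 30.9 | 29.1 |
| G2 − G1 | 27.9 | 32.0 | 30.5 |
| G3 − G1 | −0.7 | +1.1 | +1.4 |

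Any single awake value shared by all groups gives back the raw contrasts exactly. G3 − G1 changes sign with the reference, but all three values are small against the Table VIII standard error of 3.9766.

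**6. Are the first samples comparable?** Welch 95% intervals for the difference in sample 1: G2 − G1 4.1 (−4.7 to 12.9), G2 − G3 2.3 (−6.9 to 11.5), G3 − G1 1.8 (−2.7 to 6.3). One-way ANOVA from the rounded summaries gives p = 0.41 and Welch ANOVA 0.44, against 0.58 in Table II; another test may have been used, and the conclusion is the same. No imbalance is shown, but a G2 difference of about 10 mmHg from either other group is not excluded.

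**The case against.** The best defence is that little depends on the first sample. Every PaCO2 comparison in the protocol's tables uses raw values at a given time, item 2 promises intervals for raw data as well as for change, and no baseline adjustment is planned. That stands, and it limits the harm to change-from-baseline results and the before-surgery rows of Table II.

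Stronger readings are tempting, and the text does not support them:

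- *Each group is sampled at a different anaesthetic stage.* Not forced. G2 and G3 can both be read as before loss of consciousness, and G1 may be sampled awake.
- *The group comparison is biased.* Not shown. If only G1 were sampled after hypnosis and relaxant, one would expect its first PaCO2 to be the highest; it has the lowest mean and the smallest SD. With groups this small, that settles nothing either way. The excess over recovery is similar across groups and largely cancels in the contrasts.
- *The rise is understated by more than half.* That holds for G1 (5.9/10.8 = 55%) and G3 (8.0/12.2 = 66%), but not G2 (8.5/41.3 = 21%), and only if recovery is the undisturbed level. That sample comes 15 minutes after arrival in recovery, after sedatives and opioid, in patients transferred on an oxygen mask.

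The reverse inference fails too: p = 0.58 with 7 to 11 patients per group does not establish comparable baselines.

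**Conclusion.** The point holds as a defect in the sampling rule, not as a demonstrated bias. The protocol fixes group-specific landmarks and no common stage, so change from baseline lacks a shared reference in groups compared on CO2 retention. On interim means, using change from baseline instead of raw values lowers G2 − G3 by 2.3 mmHg (30.9 to 28.6) and G2 − G1 by 4.1 mmHg (32.0 to 27.9). The large G2 effect stands either way. Separately, the first-sample mean exceeds recovery in all groups by 5.9 to 8.5 mmHg, so change from the first sample may understate the total rise, provided recovery approximates the undisturbed level. The protocol gives no awake sample with which to test that. The rule should be corrected before more patients are sampled.

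**What to change.** - **Remaining 61 patients:** in section C and on the case report form, define one first-sample point relative to the start of anaesthesia, identical in all three groups, and replace the three group-specific triggers with it. The investigators choose the point; what matters is that it is common and unambiguous.
- **All 90 patients:** name raw PaCO2 at the end of the operation as the main between-group CO2 contrast. This matches what Tables II and VIII already do. Say openly that it was named after 29 patients had been tabulated.
- **Change from baseline:** report it as descriptive, separately for the old and the new baseline definition.

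The cost is one sentence in the methods, one form label and a line in the analysis list, with no extra samples. The radial catheter is already planned for every patient, but it must be in place by the common point; the protocol does not say when it is inserted. The real downside is that the first 29 and last 61 patients will have differently defined baselines, so change from baseline cannot be pooled over all 90.
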